21-22	Prior to evening dose and serial sampling at 1, 2, 4, 6, 8, 12, 14, 16, 18, and 24 hours after evening dose application.	Prior to evening dose and serial samples at 1, 2, 4, 6, 8, 12, 14, 16, 18 and 24 hours post dose application.	Sparse ¹ sampling as per sampling design in Table 3	Sparse ¹ sampling as per sampling design in Table 3
-------	--	---	--	--

1 The sparse blood sampling schedule for Part B (pediatrics) has been decided after generation of PK profiles in adults in Part A. The schedule consists of two sets: Set 1 with sampling time points of 0, 2, and 8 hours and Set 2 with sampling time points of 4, 12, 18, and 24 hours. Half of the subjects will follow Set 1 and other half will follow Set 2 and this assignment will be in a serial order based on the sequence of randomization for test and reference treatments across the sites. The assignment of sets will cross over between the Day 14 and Day 21, such that each subject will provide a total of 8 PK samples including Day 1 pre-dose as presented in the table below.

Table 3: Sparse Blood Sample Collection for Pharmacokinetic Analysis

Sparse sampling schedule	Day 1	Time Points in Hours (Post evening dose: Day 14 and Day 21)						
		Day 14-15			Day 21-22			
		Set 1	0 (Pre-dose)	0 (Pre-dose)	2	8	4	12
Set 2	0 (Pre-dose)	4	12	18	24	0 (Pre-dose)	2	8

TABLE OF CONTENTS

COMPLIANCE STATEMENT.....2

SIGNATURES.....2

GENERAL INFORMATION4

SYNOPSIS5

TABLE OF CONTENTS17

LIST OF TABLES19

LIST OF ABBREVIATIONS20

LIST OF DEFINITIONS21

1 INTRODUCTION.....22

2 ETHICAL CONSIDERATIONS.....22

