4 STUDY DESIGN

This will be a randomized, multiple-dose, laboratory-blinded, open-label, 2-arm, parallel-arm, multicenter study in subjects with moderate acne vulgaris.

Approximately 62 subjects will be randomized to receive either Test or Reference product, stratified by age (adult subjects: 17 years or older; pediatric subjects: 9 years to 16 years 11 months for the Test product and 12 years to 16 years 11 months for the Reference product) with approximately even distribution between males and females in each age stratum. The study will be conducted in two parts, Part A and Part B in a sequential manner. Based on full PK profiles generated for adult subjects in Part A, the sparse PK sampling design in pediatric subjects has been established in Part B. Part B (age 9 years to 16 years 11 months for DFD-03 and 12 years to 16 years 11 months for Reference) will enroll up to 38 subjects, which will include at least 6 subjects 9 to 11 years of age, and among those at least 2 subjects between 9 and 10 years of age. Target enrollment is 32 subjects, but up to 6 additional subjects may be enrolled to reach a minimum of 16 evaluable subjects, who have sparse samples collected on Day 14 and Day 21, randomized to the Test treatment.

PK profiling will be performed on Day 14 and on Day 21. Day 14 is selected as the earliest time point at which the steady state is expected to be achieved in subjects with moderate acne vulgaris, before any significant improvement in skin barrier occurs.

In Part A, 24 adult subjects will be enrolled such that 12 subjects each will be assigned to receive either Test or Reference treatment. In Part B, up to 38 subjects will be enrolled where approximately 26 subjects will receive Test treatment and 12 subjects will receive Reference treatment. Enrollment will continue until at least 16 evaluable subjects randomized to the Test treatment complete the study.

For 21 days, study product will be applied on the face, neck, upper chest, shoulders and upper back region, not exceeding 15% of the body surface area. The Test product will be applied twice daily, 12 hours apart (morning and evening; 42 consecutive doses), and the Reference product will be applied once daily in the evening (21 consecutive doses).

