Study staff should wear gloves at all times while handling or applying the study product. If powdered gloves are worn, they should be rinsed and dried prior to handling study product.

Test Product

The Test product will be applied twice daily, 12 hours apart (± 1 hour) (morning and evening), for 21 days (42 consecutive doses). Before each dose application, subjects will take a brief warm shower to wet their skin. Approximately 5 grams of the product will be applied by the subject to the face, neck, and upper chest and will be applied by a member of the clinical staff to the shoulders and upper back, and rubbed into the skin until foamy (approximately 30 seconds for the total application area). After being left on for about 1 minute, the subject will rinse off the Test product in the shower for about 1 minute. On Day 22, the last dose application in morning will not be rinsed off in the shower; however, the subject will be permitted to towel dry after the Test product has been on for approximately one minute. Twelve hours following the last application,, the subject will rinse off in the shower for 1 minute. The subject should bare their exposed body parts when the product is rinsed off and the clinical staff should ensure that no residues are left on the body.

Note: For age group 9-11 years 11 months, approximately 4 grams of test product will be applied considering their lesser BSA.

Reference Product

The Reference product will be applied to dry skin once daily in the evening for 21 consecutive days. There should be a 24 hour interval between applications (± 1 hour). Approximately 5 grams of the product will be applied by the subject to the face, neck, and upper chest and by a

member of the clinical staff to the shoulders and upper back. The applied cream will be left on for 12 hours and showering will not be permitted until at least 12 hours after the application.

All Subjects

The times of dose applications should be recorded on the case report form (CRF).

Heavy make-up used to cover-up blemishes and sunscreen should be removed before study product application using a gentle cleanser approved by the investigator, such as Cetaphil Gentle Skin Cleanser, etc.

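### Sparse-sampling sets are assigned without regard to age, so the few 9-11-year-olds may be unevenly split between the sets; alternating within age band is a cheap improvement

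*Combined protocol and SAP*

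**What the plan says.** Footnote 1 to Table 2 defines "Set 1 with sampling time points of 0, 2, and 8 hours"; its counterpart is "Set 2 with sampling time points of 4, 12, 18, and 24 hours". On the split between them it states: "Half of the subjects will follow Set 1 and other half will follow Set 2". The rule for deciding which child gets which set is that "this assignment will be in a serial order based on the sequence of randomization for test and reference treatments across the sites". It then adds that "The assignment of sets will cross over between the Day 14 and Day 21", so that "each subject will provide a total of 8 PK samples including Day 1 pre-dose". Table 3 sets this out: a child who starts in Set 1 gives 0, 2 and 8 h on Day 14 and 4, 12, 18 and 24 h on Day 21-22. A child who starts in Set 2 does the reverse.

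The youngest children are a distinct group. Section 4 caps Part B enrolment at 38 and describes the group as one "which will include at least 6 subjects 9 to 11 years of age, and among those at least 2 subjects between 9 and 10 years". Under Section 5.2 they can enter only the Test arm, and inclusion criteria 6 to 8 (lesions beyond the face, and the two facial lesion-count minima) do not apply to them. Section 6.2 states: "For age group 9-11 years 11 months, approximately 4 grams of test product will be applied considering their lesser BSA"; the other subjects receive about 5 g. Randomisation is stratified only as adult or paediatric (Section 4), and the scheme is generated for each site (Section 6.4).

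Section 11.4 plans descriptive statistics at each time point and mean concentration-time profiles. The Synopsis asks for Test versus Reference intervals on Day 14 and on Day 21.

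**The concern.** No child is sampled at all seven times on one day, so any 0-24 h paediatric profile for a given day joins values from two groups of children. If the 9-11-year-olds fall mainly in one group, the 0/2/8 h values and the 4/12/18/24 h values on that day come from different mixes of age and applied amount. Part of the apparent shape of the Test profile would then reflect who was in which set. The youngest children would also be barely represented at 3 or 4 of the 7 times that day.

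The Test dose on the morning of Day 22 is not rinsed off, whereas the one on Day 15 is. The 18 h and 24 h samples on the two days therefore describe different conditions. The left-on samples come only from children who start in Set 1, and the rinsed ones only from children who start in Set 2.

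**Working it through.** **The protocol's own figures.** Samples per child: 1 (Day 1) + 3 + 4 = 8, as stated. Part B: 26 Test + 12 Reference = 38, as stated. At the target of 32, with Reference kept at 12, Test is 32 - 12 = 20 (derived, not stated).

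**Inputs.** N is the number of Test children in Part B: 16 (minimum evaluable), 20 (target) or 26 (maximum), with N/2 in each set. k is the number aged 9-11; the minimum is 6. Assumption: their places in the randomisation sequence are random with respect to set.

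**Formula.** P(x of 6 in Set 1) = C(N/2, x) × C(N/2, 6 - x) / C(N, 6).

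| Split of 6 | N = 16 | N = 20 | N = 26 |
|---|---|---|---|
| 6:0 | 56/8008 = 0.7% | 420/38760 = 1.1% | 3432/230230 = 1.5% |
| 5:1 | 896/8008 = 11.2% | 5040/38760 = 13.0% | 33462/230230 = 14.5% |
| **At most one in a set** | **11.9%** | **14.1%** | **16.0%** |
| 4:2 | 3920/8008 = 49.0% | 18900/38760 = 48.8% | 111540/230230 = 48.4% |
| 3:3 | 3136/8008 = 39.2% | 14400/38760 = 37.2% | 81796/230230 = 35.5% |

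**Other numbers of children.** The chance of at most one in a set is 28-32% if only 5 are evaluable and 1-3% if 8 are enrolled. The minimum of 6 applies to enrolment, not to evaluability.

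**Two 9-10-year-olds in the same set.** (N/2 - 1)/(N - 1) = 7/15, 9/19, 12/25 = 46.7%, 47.4%, 48.0%. In half of these cases, about 23-24%, both start in Set 2 and that band has no left-on sample at 18 h or 24 h.

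**At most one of the 6 starting in Set 1** (almost no left-on data for ages 9-11): half of the bold row, 6-8%.

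**Other readings of serial order, 6 children.**
- Alternation on one list of 38: 17.9% with at most one in a set.
- Alternation within each of two sites: 17.1%.
- Alternation with the 6 enrolled consecutively: 0%, always 3:3.
- First half Set 1, second half Set 2, with the 6 enrolled consecutively: 80% (N = 20) to 86% (N = 26) of possible positions.

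**Effect on the applied-amount mix, N = 20 and a 5:1 split.** Mean amount is (5×4 + 5×5)/10 = 4.5 g in one set and (1×4 + 9×5)/10 = 4.9 g in the other, against 4.7 g in both at 3:3. This is applied amount only. The documents give no concentrations from which to size a bias in exposure.

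**The case against.** The best defence is the crossover. Over the two days every child gives all seven times once, so no split leaves the youngest children without data at any nominal time. The unrinsed dose changes only samples taken after it, at 18 h and 24 h. Values at 0, 2, 4 and 8 h follow rinsed doses on both days, and so does the 12 h value if it is drawn before the morning application. This stands, and it confines the part that cannot be recovered to 18 h and 24 h.

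A reader might infer that the youngest children's profile cannot be formed on either day. That is true only of a 6:0 split, at about 1%; a 5:1 split is thin but not empty. A reader might also take the 61-64% chance of any split other than 3:3 as the size of the problem. Most of that is 4:2, which still leaves two children at every time.

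No PK profile, subgroup or comparison for ages 9-11 is specified, and Section 11.1 says the study is not powered. The documents therefore do not support a claim that a planned test is invalid. Nor do they state that the age minimum exists to describe exposure in this band; that is an inference.

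Finally, the probabilities are conditional. Serial order is not defined, the allocation list is not in the documents, and nothing says how Test-only children enter the sequence. Under one plausible reading the split is always 3:3; under another, clustering is likely. This limits the precision of the figures, but it is also a reason to state the rule.

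**Conclusion.** The point holds as a cheap improvement, not as a flaw that undermines an analysis. Nothing in the documents balances a required, Test-only group with a different applied amount across the two sampling sets.

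Severe imbalance is a minority outcome. It has a 12-16% chance at the minimum of 6, assuming random positions and 16-26 Test children, and falls to 1-3% with 8. The crossover repairs most of it when the days are read together, but not at 18 h and 24 h. What is gained is a better-balanced Test profile on each day and a fuller description of the youngest children. No effect on AUC, Cmax or the Test/Reference ratio has been quantified.

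**What to change.** Amend footnote 1 to Table 2 so that sets alternate in order of randomisation within treatment and age band, from one list held across both sites. Keep Test 9-11 years separate from Test 12 years to 16 years 11 months and from Reference. Within Test 9-11, alternate separately for 9-10 years, starting with Set 1, and for 11 years, starting with Set 2.

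The opposite starts matter. With a children aged 9-10 and b aged 11, Set 1 minus Set 2 equals (1 if a is odd) - (1 if b is odd), which is always -1, 0 or 1. Both the 9-10 group and the whole 9-11 group are thus balanced to within one child. At the minima (2 and 4) the splits are 1:1 and 3:3. If both bands started with Set 1, odd counts such as 3 and 3 would give 4:2. Restarting the alternation at each site can also give 4:2 within a single 9-11 stratum.

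Do not try to repair losses by giving the next child the set of one who proves non-evaluable. Section 11.2.2 requires samples on both Day 14 and Day 21, so evaluability is known only after Day 21, when later children may already hold a set.

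The cost is a slightly more complex allocation list, issued before Part B assignment begins. No extra subjects, samples or visits are needed. Even at 1:1, the two 9-10-year-olds supply one child per time point per day, so the change prevents gaps but does not give that band a profile that can be summarised on its own.

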CFR	Code of Federal Regulations
CRF	case report form
CRO	contract research organization
FDA	Food and Drug Administration
GCP	Good Clinical Practice
IGA	Investigator's Global Assessment
IRB	institutional review board
MedDRA	Medical Dictionary for Regulatory Activities
PK	pharmacokinetic(s)
PT	preferred term
SAE	serious adverse event
SOC	system organ class
TEAE	treatment-emergent adverse event

LIST OF DEFINITIONS

Term	Definition
Screening Visit	The day a subject is screened according to the protocol inclusion/exclusion criteria and screening procedures after having provided informed consent/assent.
Screened Subject	A subject who has signed informed consent/assent.
Subject Number	A unique number assigned to a screened subject. The number consists of the 3-digit unique site number followed by a 3-digit sequential number for each subject in chronological order (e.g., 206001, 206002, where the site number is 206 and the first and second screened subjects at site 206 are 001 and 002, respectively).
Study product(s)	Investigational product(s)

1 INTRODUCTION

Tazarotene, an acetylenic retinoid, is a prodrug that undergoes rapid and complete metabolism to its active metabolite tazarotenic acid ([Chandraratna, 1996](#)). Retinoids are a class of keratolytic drugs derived from retinoic acid used for the treatment of acne and psoriasis. Several synthetic retinoids have been developed for topical treatment of acne.

Tazarotene was initially developed in gel formulation and subsequently in cream and foam formulations. Products containing tazarotene have been proven to be effective in the treatment of acne vulgaris and psoriasis, as well as being effective in the mitigation (palliation) of facial fine wrinkling, facial mottled hyper- and hypopigmentation, and benign facial lentiginosities.

[name] has developed DFD-03 Lotion, a new formulation containing 0.1% tazarotene for the topical treatment of acne vulgaris. This new product is intended to be used as a face wash twice daily. Treatment use will begin by applying a generous amount of product to moistened affected skin, rubbing until foamy, and then rinsing with water after 1 minute.

Acne vulgaris is characterized by a mixture of inflammatory lesions (papules, pustules, and nodular cystic lesions) and non-inflammatory lesions (open and closed comedones) ([Shalita, 2004](#)). The four primary factors contributing to acne are abnormal follicular epithelial desquamation, hyperactivity of the sebaceous glands, proliferation of *Propionibacterium acnes*, and perifollicular inflammation.

Currently available treatments for acne vulgaris include oral and topical antibiotics, topical benzoyl peroxide, topical salicylic acid, topical adapalene, topical azelaic acid, topical dapsone, oral and topical retinoids (including tazarotene), and phototherapy.

Tazarotene is a well-characterized active ingredient, and many studies have been conducted on its pharmacology, toxicology and clinical efficacy and safety ([Fabior Prescribing Information](#), [Tazorac Cream Prescribing Information](#)).

Tazarotene is characterized by the FDA as a Category X drug, indicating that it may or can cause fetal harm when administered to a pregnant woman and is contraindicated in women who are or may become pregnant ([Menter, 2000](#)). At least 6 women are known to have become pregnant during clinical studies with tazarotene and all reported the birth of healthy babies, although the timing and extent of exposure in relation to the gestation time are unknown in these cases.

The purpose of this study is to compare the bioavailability of tazarotene and tazarotenic acid after twice-daily application of DFD-03 Lotion with that after once-daily application of Tazorac Cream, with products applied for 21 days.

More information about DFD-03 Lotion can be found in the Investigator's Brochure.

2 ETHICAL CONSIDERATIONS

2.1 Institutional Review Board Review

The protocol, protocol amendments, subject recruiting materials, the informed consent form, and any other materials provided to subjects must be approved by an institutional review board (IRB) operating in compliance with 21 Code of Federal Regulations (CFR) Part 56. A copy of

the approval letter must be received by the sponsor or contract research organization (CRO) prior to shipment of drug supplies to the site.

Records of the IRB's review and approval of all documents pertaining to the study must be kept on file by the investigator and are subject to sponsor and Food and Drug Administration (FDA) inspection at any time.

2.2 Ethical Conduct of Study

The investigator will ensure that this study is conducted in full conformity with the principles set forth in 21 CFR Part 50 – Protection of Human Subjects and in the Declaration of Helsinki (2013) (see [Appendix 1](#)).

2.3 Informed Consent

Written informed consent must be obtained before a subject can participate in the study, prior to performing any study related procedures, and before withdrawal of any therapies prohibited during the study. Informed consent is a process that is initiated prior to the subject's agreement to participate in the study and continuing throughout the subject's study participation. The process involves an extensive discussion with the subject about the study procedures and the risks and possible benefits of participation in the study.

For subjects under the age of majority in the state they are enrolled, the subject's parent or legal guardian will be required to sign the informed consent form and the subject will sign an IRB-approved "Information and assent" form before the subject is enrolled into the study.

A copy of the signed consent form and "Information and assent" form (when applicable) will be given to every subject and the original will be maintained with the subject's records.

2.4 Selection of Investigators

Investigators for the study should be board-certified dermatologists licensed in the state where the study is being conducted, with knowledge and understanding of Good Clinical Practice (GCP) and experience in treating acne vulgaris. In some cases, qualified physicians who are not board-certified dermatologists may participate based on training and experience in the treatment of acne vulgaris. Sub-investigators may be licensed physicians, physician assistants, or nurse practitioners with experience in treating acne vulgaris or in dermatology and a good understanding of GCP. Investigators may delegate study tasks to other site personnel if they are qualified to perform the task.

3 STUDY OBJECTIVES

The primary objective of this study is to evaluate the comparative bioavailability of tazarotene and tazarotenic acid after twice-daily application of DFD-03 Lotion (Test product) versus once-daily application of Tazorac Cream (Reference product) for 21 days in Patients with moderate acne vulgaris.

The secondary objectives are

- a) Assessment of disease severity at baseline and at the pharmacokinetic (PK) sampling days for each treatment.
- b) To determine the safety and tolerability of each treatment.

4 STUDY DESIGN

This will be a randomized, multiple-dose, laboratory-blinded, open-label, 2-arm, parallel-arm, multicenter study in subjects with moderate acne vulgaris.

Approximately 62 subjects will be randomized to receive either Test or Reference product, stratified by age (adult subjects: 17 years or older; pediatric subjects: 9 years to 16 years 11 months for the Test product and 12 years to 16 years 11 months for the Reference product) with approximately even distribution between males and females in each age stratum. The study will be conducted in two parts, Part A and Part B in a sequential manner. Based on full PK profiles generated for adult subjects in Part A, the sparse PK sampling design in pediatric subjects has been established in Part B. Part B (age 9 years to 16 years 11 months for DFD-03 and 12 years to 16 years 11 months for Reference) will enroll up to 38 subjects, which will include at least 6 subjects 9 to 11 years of age, and among those at least 2 subjects between 9 and 10 years of age. Target enrollment is 32 subjects, but up to 6 additional subjects may be enrolled to reach a minimum of 16 evaluable subjects, who have sparse samples collected on Day 14 and Day 21, randomized to the Test treatment.

PK profiling will be performed on Day 14 and on Day 21. Day 14 is selected as the earliest time point at which the steady state is expected to be achieved in subjects with moderate acne vulgaris, before any significant improvement in skin barrier occurs.

In Part A, 24 adult subjects will be enrolled such that 12 subjects each will be assigned to receive either Test or Reference treatment. In Part B, up to 38 subjects will be enrolled where approximately 26 subjects will receive Test treatment and 12 subjects will receive Reference treatment. Enrollment will continue until at least 16 evaluable subjects randomized to the Test treatment complete the study.

For 21 days, study product will be applied on the face, neck, upper chest, shoulders and upper back region, not exceeding 15% of the body surface area. The Test product will be applied twice daily, 12 hours apart (morning and evening; 42 consecutive doses), and the Reference product will be applied once daily in the evening (21 consecutive doses).

Subjects will visit the clinical site daily prior to each dose application. Subjects will be confined at the clinic on Day 1 from prior to the evening dose until after that dose, from prior to the evening dose on Day 14 to after the evening dose on Day 14, and from prior to the evening dose on Day 21 to after the 24-hour post dose PK sample collection on Day 22. Subjects will leave the clinic after completion of clinical activities. On Days 14 and 21, blood sampling for PK estimation will be performed over an interval of 24 hours. Adequate trough samples will be collected at the evening visit on Day 1 to assess baseline and on days 12, 13, 14, 19, 20 and 21 to assess attainment of steady state. For the pediatric population in part B, the trough samples will not be collected on days 12, 13, 19 and 20. Any subject missing dosing of any one dose of Reference product and two consecutive doses of Test product between days 1 and 8, or between days 8 and 15 will be considered for steady state estimation at Day 14, or Day 21, respectively. Subject (s) missing either two consecutive dosing days (two doses for reference and four for test product) between day 1 and 8 or missing two non-consecutive dosing days between Day 2 and Day 11 will be assessed for steady-state estimation at Day 21. Subjects missing dosing between Days 12 and 14 and between Days 19 and 21 will not be considered for steady-state estimation or PK and statistical analysis.

For all dosing days (except confinement days), subjects will come to the clinical site ± 1 hour of each dose application (e.g., around 7:00 pm and 7:00 am) for twice-daily application of Test product and (e.g. around 7:00 pm) for once-daily application of Reference product. Subjects will leave the clinical site after completion of the scheduled activities. On Day 14 and Day 21, subjects will report to the clinical site before scheduled dosing, allowing sufficient time for all pre-dosing assessments to be performed.

Blood samples for PK estimation will be collected (within time window ± 15 minutes) at scheduled intervals over a period of 24 hours after the evening dose application for Test product and Reference product on Day 14 and Day 21. On Day 22, for assessment of leave on exposure for 12 hours, the last dose application of Test product (morning dose on Day 22) will not be rinsed off.

Plasma samples for analysis of tazarotene and tazarotenic acid plasma concentrations will be collected on the schedule described in [Table 2](#). The PK parameters of interest will be $T_{\max(ss)}$, $C_{\max(ss)}$, $AUC_{(ss)}$, $C_{\min(ss)}$.

For Part B of study, plasma concentration data generated from sparse samples (maximum of 4 time points from each subject, [Table 3](#)) on Day 14 and Day 21 will be used for calculation of PK parameters: $C_{\max(ss)}$, $AUC_{(ss)}$, $C_{\min(ss)}$.

Disease severity will be assessed by IGA score and inflammatory and non-inflammatory lesion count (% change from baseline for lesion counts) at Day 15 and Day 21/Day22.

Safety assessments will include adverse events (AEs), the investigator's assessment of application site reactions (dryness, non-lesional erythema, peeling, stinging, burning, and itching), clinical safety laboratory evaluations (chemistry, hematology, and urinalysis), and physical examination including vital signs (blood pressure and pulse rate).

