Approximately 62 subjects will be randomized to receive either Test or Reference product, stratified by age (Adult subjects: 17 years or older; Pediatric subjects: 9 years to 16 years 11 months for the Test product and 12 years to 16 years 11 months for the Reference product) with approximately even distribution between males- and females in each age-strata. The study will be conducted in two parts, Part A and Part B in a sequential manner. Based on full PK profiles generated for adult subjects in Part A, the sparse PK sampling design in pediatric population has been established in Part B.

Part B (age 9 years to 16 years 11 months for DFD-03 Lotion arm and age 12 years to 16 years 11 months for Tazorac Cream arm) will enroll up to 38 subjects, which will include at least 6 subjects 9 to 11 years of age, and among those at least 2 subjects between 9 and 10 years of age. Target enrollment is 32 subjects, but up to 6 additional subjects may be enrolled to reach a minimum of 16 evaluable subjects, who have sparse samples collected on Day 14 and Day 21, randomized to the Test treatment.

PK profiling will be performed on Day 14 and on Day 21. Day 14 is selected as the earliest time point at which the steady state is expected to be achieved in subjects with moderate acne vulgaris, before any significant improvement in skin barrier occurs.

In Part A, 24 adult subjects will be enrolled such that 12 subjects each will be assigned to receive either Test or Reference treatment. In Part B, up to 38 subjects will be enrolled where approximately 26 subjects will receive Test treatment and 12 subjects will receive Reference treatment. Enrollment will continue until at least 16 evaluable subjects randomized to the Test treatment in Part B complete the study.

For 21 days, study product will be applied on the face, neck, upper chest, shoulders and upper back region, not exceeding 15% of the body surface area. The Test product will be applied twice daily, 12 hours apart (morning and evening; 42 consecutive doses) and the Reference product will be applied once daily in the evening (21 consecutive doses).

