7.7 Early Withdrawal of Subjects

- Subjects should be withdrawn from the study if they no longer wish to participate, are being uncooperative, or if the investigator feels that it is in the best interest of the subject to withdraw.
- Subjects with protocol deviations or who were later discovered to not have met exclusion criteria should not be withdrawn unless there is a safety concern. The protocol deviation should be recorded in the subject’s chart and Protocol Deviation Form and included in the study report.
- Subjects who experience an AE resulting in or requiring discontinuation of study product use should be encouraged to be followed in the study until the AE is resolved or stabilized.

4. If a female subject becomes pregnant during the study, study product will be discontinued immediately and she will be followed through the pregnancy and delivery. Details of the pregnancy, delivery and health of the infant should be recorded on the Pregnancy Report Form and the sponsor notified immediately.
5. At the time of study discontinuation, the investigator will record the reason for early withdrawal, date of last dose application, date of last visit or contact, collect AE data, and, if possible, perform all Day 21 visit-specific evaluations. Every attempt should be made to contact subjects who are lost-to-follow-up for a final safety assessment. At least three attempts must be documented in the subject's chart including the use of at least 1 certified letter. Any contact, either direct or indirect, should be made with the purpose to document the final status of the subject with regard to safety.
6. Subjects who withdraw early will not be replaced.

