11.2.2 Pharmacokinetic Analysis Population

Samples from all subjects who provide evaluable data will be assayed; these subjects will be included in the PK and statistical analysis. In order to be considered evaluable, a subject must have PK samples collected on both Day 14 and Day 21. An unequal number of subjects per arm will be used.

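### Part B counts its 9-11-year-olds at enrolment but stops on 16 evaluable Test children of any age, so it can end short of evaluable subjects in the youngest band

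*Combined protocol and SAP*

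**What the plan says.** Section 4 and the Synopsis cap Part B at 38 and set two age minima: "at least 6 subjects 9 to 11 years of age, and among those at least 2 subjects between 9 and 10 years of age". Both numbers describe who is enrolled.

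The target for Part B is 32, and "up to 6 additional subjects may be enrolled to reach a minimum of 16 evaluable subjects" on Test. The Synopsis then says: "Enrollment will continue until at least 16 evaluable subjects randomized to the Test treatment in Part B complete the study". Section 4 gives the same rule without naming Part B: "Enrollment will continue until at least 16 evaluable subjects randomized to the Test treatment complete the study". Neither version has an age condition.

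Section 7.7 item 6 adds: "Subjects who withdraw early will not be replaced".

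Under Section 11.2.2, to be evaluable "a subject must have PK samples collected on both Day 14 and Day 21", and evaluable subjects enter the PK and statistical analysis. Sections 4 and 6.3 separately exclude from that analysis subjects who miss dosing in the Day 12-14 and Day 19-21 windows. Section 11.2.2 does not refer to this exclusion.

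**The concern.** The protocol singles out the 9-11 band with its own minimum, but the minimum no longer binds once the child is enrolled. If a 9-11-year-old withdraws or is not sampled on one of the PK days, an evaluable adolescent can fill the gap in the count of 16. Nothing directs the extra places to the younger band.

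Adolescents are not straightforward substitutes. Children aged 9 to 11 years 11 months receive about 4 g rather than 5 g per application (Section 6.2) and are exempt from inclusion criteria 6 to 8 (Section 5.2). Section 11.1 offers no power calculation; it justifies the sample size by adequate representation of the paediatric and adult populations. An enrolment-only minimum does not secure that representation in the PK data for the youngest band. A shortfall cannot be repaired once enrolment has closed.

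**Working it through.** **Stated totals.** Part A 24 + Part B 38 = 62. Part B at the cap: 26 Test + 12 Reference = 38, and 32 + 6 = 38. These agree. The 16, 6 and 2 are given without derivation.

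**Inputs.** Reference starts at 12 years (Section 5.2, criterion 3), so every 9-11-year-old is on Test. Test places are 32 - 12 = 20 at target, assuming all 12 Reference places are filled, and 38 - 12 = 26 at the cap. Suppose exactly 6 children aged 9-11 are enrolled, 2 of them aged 9-10.

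**Counting bound (no loss rate needed).** Fewest evaluable 9-11-year-olds consistent with 16 evaluable = max(0, 16 - older Test children).
- 20 Test places: 20 - 6 = 14 older; 16 - 14 = 2.
- 22 Test places: 16 older; bound 0.
- 26 Test places: 20 older; bound 0.

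**Chance of a shortfall.** Let d be the probability that a child is not evaluable, independent and equal across ages. The protocol gives no value; 5% to 20% is an assumption.
- Fewer than 6 of 6: 1 - (1 - d)^6.
- Fewer than 2 of 2: 1 - (1 - d)^2.
- 16 reached but fewer than 6 young evaluable: the sum over y = 0 to 5 of P(y of 6 young evaluable) x P(at least 16 - y older evaluable).

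| | d = 5% | d = 10% | d = 20% |
|---|---|---|---|
| Fewer than 6 of 6 aged 9-11 | 1 - 0.735 = 26% | 1 - 0.531 = 47% | 1 - 0.262 = 74% |
| Fewer than 2 of 2 aged 9-10 | 1 - 0.9025 = 10% | 1 - 0.81 = 19% | 1 - 0.64 = 36% |
| 16 met, fewer than 6 young, 20 Test, no top-up | 26% | 43% | 40% |
| 16 met, fewer than 6 young, 26 Test | 26% | 47% | 73% |

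In the third row the last value dips because, at 20% loss, 20 Test subjects reach 16 only 63% of the time.

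**Sampling density.** Half the subjects follow each sampling set on a PK day (Table 2 footnote), so 6 children give about 6/2 = 3 values per time point. One loss takes the affected time points from about 3 values to about 2. Sets are assigned by randomization order, not by age, so even a 3/3 split is not assured.

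**Room under the cap.** For at least 90% probability of 6 evaluable, the number aged 9-11 to enrol is 7, 8 or 9 at 5%, 10% or 20% loss (attained probability 96%, 96%, 91%). For 2 evaluable aged 9-10 it is 2, 3 or 4 (90%, 97%, 97%). All fit within 26 Test places.

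**Definition.** A child with samples on both Day 14 and Day 21 who missed doses in the Day 12-14 and Day 19-21 windows is evaluable under Section 11.2.2 and excluded from PK analysis under Sections 4 and 6.3. Such a child counts toward the 16 without adding to the analysis.

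**The case against.** The strongest reply is that no planned analysis needs 6 evaluable young children. Section 11.4 compares treatments and specifies no estimate for ages 9-11, and Section 11.1 disclaims powering, so an enrolment minimum may be all that was meant. The first part stands: the primary comparison does not depend on this, and no stated number is breached. But representation is the only rationale given for the sample size, and in a PK study it is useful only if the child contributes PK data.

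Sites may also enrol more than 6, and heavy loss seems unlikely over 21 days with every application at the clinic. Both are fair, but nothing requires the larger number, and even 5% loss gives a 26% chance of falling below 6.

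A reader might infer several stronger points that the documents do not support:
- **An expected loss of 20% or 38%, from 16/20 or 16/26.** These ratios divide a minimum by a target or a ceiling. They show how much loss the plan tolerates, not what it expects.
- **Almost no PK data under 12 years, or empty time points.** At 20% loss the expected number evaluable is 6 x 0.8 = 4.8, at least 4 of 6 has probability about 90%, and 0 or 1 of 6 about 0.2%. Losing one child thins the time points; it does not by itself empty them.
- **12 Test adults plus 4 children satisfying Section 4.** The same section ties the 16 to subjects with sparse samples, which adults do not give, and the Synopsis names Part B.
- **A single sample per day being enough.** Section 4 speaks of sparse samples on both days and requires completion of the study.
- **A direct contradiction between Section 7.7 item 6 and the extra places.** Not replacing individuals can coexist with a prespecified allowance, though the protocol should say how.

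**Conclusion.** The concern holds as a gap in the stopping rule. Part B can follow its text exactly and close with fewer than 6 evaluable children aged 9-11, or fewer than 2 aged 9-10. The counting bounds (2 at 20 Test places, 0 at 26) assume exactly 6 enrolled and, for 20, a full Reference arm. They show what the rule permits and are not forecasts. The probabilities (26/47/74% and 10/19/36%) depend on the assumed 5/10/20% loss, taken as independent and equal across ages. 'Too few' is measured against the protocol's own 6 and 2, since it states no evaluable minimum for this band. The mismatch between the evaluable definition and the missed-dose exclusions is a separate, smaller defect that can inflate the count of 16. The changes are worth making while Part B is still enrolling.

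**What to change.** Amend the protocol as follows:

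1. State the minima as evaluable subjects: at least 6 evaluable aged 9-11, of whom at least 2 aged 9-10.
2. End Part B enrolment when these minima and the 16 are all met, or when the cap of 38 is reached. Use the up-to-6 extra places first for the age band that is short.
3. In Section 11.2.2, define evaluable for Part B as having sparse samples on both Day 14 and Day 21 and not being excluded from PK analysis by the missed-dose rule. Do not require every scheduled sample: one missed draw would then make a child non-evaluable and worsen the shortfall.
4. Reconcile Section 7.7 item 6 with the extra places in Section 4.
5. As an editorial point, name Part B in the Section 4 stopping sentence, as the Synopsis does.

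The cost is amendment wording; the cap does not change. The downside is that some extra places are reserved for a band that may be slower to recruit, and enrolment may run closer to the cap. If the cap is reached first, the shortfall remains and should be reported.
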